12.2.5. Subject Questionnaires

Information about the subject's PBC disease history (ie, date of diagnosis, treatment history, pruritus history, signs and symptoms, and including smoking history) will be collected during Screening. At subsequent study visits (see [Section 7.1.2](#)), subjects will be asked to complete the following questionnaires; they may be asked to initial and date to document confirmation of their responses, and the questionnaires should be filed in the subject's study records. These may require transcription to the CRF by study site staff.

- 5-D Pruritus Questionnaire: This is a questionnaire that has been validated in several different diseases. It assesses symptoms in terms of 5 domains: degree, duration, direction, disability and distribution ([Elman 2010](#)).
- Pruritus VAS: A Visual Analogue Scale (VAS) will also be used to assess pruritus in individual subjects.

12.2.6. Laboratory Assessments

Subjects will be instructed to attend any study or unscheduled laboratory visits (except Screening) in a fasted state, and subjects should remain fasted until their blood samples have been collected. At each visit, the Investigator or designee will verify that the subject has fasted for at least 8 hours and record fasting status in the source and CRF. If the subject reports having eaten (water is permitted) within 8 hours, the Investigator or designee will document accordingly in the source and CRF and remind the subject that fasting is required prior to all study visits.

Blood samples for serum chemistry and hematology will be collected at every visit as detailed in the Schedule of Study Procedures ([Section 7.1.2](#)). The number and volume of samples to be collected at each visit will be detailed in the laboratory manual.

Full instructions concerning the number and type of samples to be collected at each visit, the required sample volumes, sample collection methods, sample processing, labeling, and shipping will be provided by the central clinical laboratory in a study specific laboratory manual. All necessary collection supplies will be provided by the central laboratory and will be appropriately assembled for the specific evaluations required at each visit.

All subjects with laboratory tests containing clinically significant abnormal values are to be followed regularly until the values return to normal ranges; until a valid reason, other than investigational product-related AE, is identified; or until further follow up is deemed medically unnecessary.

Laboratory samples will be stored for a maximum of up to 1 year after the end of the study (depending on stability) in the event that retesting is required, and destroyed after 1 year if not analyzed.

The list of laboratory analytes to be tested is shown in Table 12, and the normal reference ranges for liver biochemistries are shown in [Appendix C](#).

Table 12: List of Laboratory Analytes to be Tested

Laboratory Assessment	Analyte
Serum Chemistry	Albumin, blood urea nitrogen (BUN), creatinine, direct bilirubin, total bilirubin, aspartate aminotransferase [AST, SGOT], alanine aminotransferase [ALT, SGPT], ALP, GGT, electrolytes [calcium, chloride, potassium, sodium], glucose, total protein, and blood lipids (total cholesterol, LDL, HDL and very low-density lipoprotein [VLDL] fractions and triglycerides [TG]), magnesium, phosphorus, bicarbonate, unconjugated (indirect) bilirubin, conjugated (direct) bilirubin, free fatty acids
Hematology	Hemoglobin, hematocrit, white blood count with differential, neutrophils, lymphocytes, monocytes, eosinophils, basophils, platelets, red blood cell count (including MCV, MCH, MCHC)
Coagulation	Prothrombin time (PT), partial thromboplastin time (PTT), international normalized ratio (INR)
Urinalysis	pH, specific gravity, total protein, glucose, ketones, bilirubin, blood, microscopic exam, urobilinogen, albumin, creatine, leucocytes, nitrates, albumin/creatinine ratio (if positive)
Markers of Cholecystitis and Pancreatitis	amylase and lipase
Biomarkers of Hepatic Fibrosis and/or Inflammation	IgM, C-reactive protein (CRP), TNF- α , FGF-19, CK-18, ELF, and others as determined during course of study
Genetics	DNA including single-nucleotide polymorphisms (SNPs) that may be involved in PBC; RNA
Other	OCA (parent and conjugates [glyco and tauro], OCA-glucuronide) and C4

The Investigator should manage subjects with clinically significant lipoprotein abnormalities using local standard of care procedures as appropriate after assessing the individual subject's total cardiovascular risk profile.

Urine-based β -hCG pregnancy tests will be performed in female subjects of childbearing potential per protocol specified visits. If a urine pregnancy test is positive, a serum pregnancy test must be performed to confirm the result. If positive, the Sponsor must be notified and the subject will be followed, as outlined in [Section 12.1.11](#) through pregnancy outcome.

MELD scores and Child-Pugh score will be calculated at screening, and at all visits based on serum chemistry and coagulation.

13. STATISTICAL METHODS

A statistical analysis plan (SAP), providing details about the specific planned analyses and hypothesis tests, will be prepared and approved by the Sponsor and its designees prior to the first interim analysis, propensity score determination, and unblinding of the double-blind subject treatment assignments.

13.1. Efficacy Analysis

13.1.1. Analysis Populations

The following subject populations will be evaluated and used for presentation and analysis of the data:

- The Intent-to-Treat (ITT) Population will include all randomized subjects who receive any amount of investigational product (OCA or placebo). The ITT Population will be the primary population used for efficacy analyses. Treatment assignment will be based on the randomized treatment.
- The Per Protocol (PP) Population will include all ITT subjects who do not have any major protocol violations that potentially affect the efficacy conclusion. Treatment assignment will be based on the randomized treatment.
- The Safety Population will include all subjects who received any amount of investigational product (placebo or OCA). The Safety Population will be the primary population used for safety analyses. Treatment assignment will be based on the treatment actually received.
- The PK Population will include all OCA subjects who have at least one confirmed fasted analyzable sample. Subjects must have been fasting for approximately 8 hours prior to the visit and must not have any major protocol deviations that potentially affect exposure levels. The PK population will be used for OCA PK analyses.
- The Overall Historical Control Population will include subjects from the United Kingdom (UK) -PBC Group and Global PBC Study Group databases with demonstrated comparability to randomized subjects in this clinical study (747-302) with respect to both subject characteristics and disease progression.
- The UK-PBC Historical Control Population will include subjects from the UK-PBC Group databases with demonstrated comparability to randomized subjects in this clinical study (747-302) with respect to both subject characteristics and disease progression.

- The Global PBC Historical Control Population will include subjects from the Global PBC Study Group database with demonstrated comparability to randomized subjects in this clinical study (747-302) with respect to both subject characteristics and disease progression.

13.1.1.1. Comparability of Historical Controls

Utilization of both historical control/observational databases (UK-PBC and Global PBC Study Group), with more than 6000 subjects each, allow for a rigorous subject level meta-analysis. The historical databases include long-term follow up, detailed subject-level information such as baseline clinical characteristics, longitudinal liver biochemistry, and long-term outcomes, and span a broad range of subject characteristics that may influence disease (disease state, age, gender, and regional differences in standard of care). Historical controls from both databases will be chosen based on the same study inclusion/exclusion criteria. Propensity score matching method will be utilized to select historical controls that match the treated subjects using available covariates. The adequacy of matching will be assessed by statistical methods described under [Section 13.1.8](#).

13.1.2. Determination of Sample Size

The target population is subjects who are at higher risk of liver-related clinical complications. Eligible subjects will have a diagnosis of PBC with bilirubin levels $>ULN$ and $\leq 5x ULN$ and/or $ALP > 3 \times ULN$. The following assumptions were used in sample size calculations:

- Exponential survival curves, placebo survival estimate of 0.6 at 8 years with a hazard ratio of 0.60, and total study duration of 10 years (from first subject enrolled), allowing for 4 years of subject accrual and 6 years of follow up.
- Subjects will be randomized in a 1:1 ratio to placebo or OCA.
- The 2 groups will be compared using a 2-sided log rank test at the 5% level of significance.
- Two interim analyses and one final analysis are planned. The first interim analysis will be performed when 50% of the target events are accrued and the second interim will be performed when 75% of the target events are accrued.
- A dropout rate of 10% is assumed

Based on the randomization ratio, significance level, and assumed hazard ratio, a total of 127 events (both groups combined) will provide 80% power to demonstrate a statistically significant difference between OCA and placebo on time to liver-related outcomes, including all-cause mortality.

In addition, based on the remaining assumptions stated above, it is estimated that approximately 428 subjects will be enrolled to attain 127 events.

13.1.2.1. Sample Size Monitoring

Conducting a long-term outcomes study given the low disease prevalence, relatively slow disease progression, and ethical considerations, which in combination will impact recruitment

and event rates, is inherently difficult. As stated in ICH E9, in long-term trials there is an opportunity to check the assumptions that underlay the original design and sample size calculations. The power stated above depends on the total number of events. Thus, the overall survival function can be estimated without unblinding.

Therefore, the aggregate event rate and sample size based on recruitment and retention will be evaluated quarterly in a blinded manner. This evaluation will determine if any increases in number of subjects are required in order to obtain a total of 127 adjudicated events for the final analysis in the combined groups. Specifically, the pooled number of events will be available during the study in a blinded manner, without any knowledge of the comparative efficacy in the treatment groups. This method for evaluating the sample size does not inflate the type I error rate. Additional subjects may be enrolled as appropriate.

13.1.3. Primary Efficacy Analysis

The primary efficacy endpoint will be the time to first occurrence of one of the following post-randomization:

- Death (all-cause)
- Liver transplant
- MELD score ≥ 15
- Hospitalization (as defined by a stay of 24 hours or greater) for new onset or recurrence of:
 - Variceal bleed
 - Hepatic encephalopathy (as defined by a West Haven score of ≥ 2)
 - Spontaneous bacterial peritonitis (confirmed by diagnostic paracentesis)
- Uncontrolled ascites (diuretic resistant ascites requiring therapeutic paracentesis at a frequency of at least twice in a month).

The primary efficacy analysis will compare OCA to placebo with respect to the primary efficacy endpoint using the ITT population. Only adjudicated events will be included in analyses. The 2 treatment groups will be compared using the log rank test stratified by the randomization stratification factor. Kaplan-Meier (KM) estimates of the distribution of the time-to-event will be tabulated and graphed by treatment group. The tabulation will include the KM estimate of the medians and corresponding 95% confidence intervals (CIs), if the medians can be estimated. The number and percent of subjects censored and with events will be presented. The hazard ratio and 95% CI will be determined based on a Cox regression model stratified by randomization strata to estimate the magnitude of the effect. The same analyses for primary efficacy endpoints will be performed for PP population as a sensitivity analysis.

13.1.4. Key Secondary Efficacy Analyses

The key secondary efficacy endpoints will compare OCA to placebo on the following:

- Time to first occurrence of MELD score ≥ 15

- Time to liver transplant or death (all-cause)
- Change from Baseline in total bilirubin at end of study
- Change from Baseline in ALP at end of study

The key secondary efficacy analyses will compare OCA to placebo in the ITT population with respect to the key secondary efficacy endpoints. Only adjudicated events will be included in time-to-event analyses. The comparison (hypothesis testing) will be conducted as specified in [Section 13.1.10](#) in a sequential closed testing gate-keeping procedure, provided that the primary efficacy endpoint comparison is statistically significant in favor of the OCA treatment group. If the primary comparison is not statistically significant then comparison of the secondary endpoints will be considered as descriptive and exploratory. This procedure controls the study-wise type I error.

The 2 treatment groups will be compared using the same methodology as specified for the primary efficacy analysis ([Section 13.1.3](#)). The same analyses for key secondary efficacy endpoints will be performed for PP population as a sensitivity analysis.

Analyses of change from Baseline to end of study in ALP and total bilirubin will be compared between treatment groups using analysis of covariance (ANCOVA) with change from Baseline as the dependent variable including treatment group and randomization stratification factor as fixed effects and the Baseline values as a covariate. The same analysis will be carried out using percentage change from Baseline as the dependent variable.

Descriptive statistics of the laboratory values will be summarized by treatment group. The results, change from Baseline, and percentage change from Baseline values as well as estimates of least-square means, standard errors, and 95% CIs will be presented by treatment group. Estimates of the mean difference between treatment groups, the standard error of the difference, and 95% CI of the difference will be presented.

13.1.5. Additional Secondary Efficacy Analyses

The following time-to-event secondary efficacy analyses will compare OCA versus placebo using the ITT population:

- Time to each component of the primary efficacy endpoint (except MELD score ≥ 15 which is captured above)
- Time to development of varix/varices
- Progression to cirrhosis
- Time to occurrence of HCC
- Time to liver-related death
- Time to liver-related death or liver transplant
- Time to liver-related death, liver transplant, or MELD score ≥ 15

The same analysis methodology as used for the primary efficacy analysis will be used for these secondary efficacy analyses. Similar endpoints, where available, will be analyzed to compare OCA to historical controls as described below in [Section 13.1.8](#).

Analyses of changes in liver biochemistry (GGT, ALT, AST, conjugated bilirubin, albumin, and INR) will be summarized and analyzed using the same methodology as specified in [Section 13.1.4](#) for the key secondary analyses of change in ALP and total bilirubin.

Progression to cirrhosis will be assessed in the subset of subjects considered noncirrhotic at Baseline using available medical history, clinical, and laboratory assessments as well as baseline TE, where available. Specifically, subjects with no clinical, laboratory, or radiological evidence of cirrhosis at baseline and/or a TE liver stiffness of <16.9 kPa ([Corpechot 2012](#)) will be considered noncirrhotic (See [Section 7.5.4](#)). Progression to cirrhosis will be assessed by the development of clinical, laboratory, or radiological evidence of cirrhosis and/or when liver stiffness increases to ≥ 16.9 kPa during the study in which case histological progression to cirrhosis should be confirmed by biopsy unless not medically indicated. Using this definition for progression to cirrhosis, the percentage of noncirrhotic subjects progressing to cirrhosis during the treatment period will be summarized by treatment group and compared using a Cochran-Mantel-Haenszel test stratified by the randomization stratification factor.

For those subjects enrolled in the biopsy substudy (defined in Addendum 2) progression to cirrhosis identified by the above criteria and improvement in fibrosis/cirrhosis will be confirmed by paired biopsy. Analyses for the histological assessment conducted as part of the biopsy substudy are defined in Addendum 2).

Analyses of changes in MELD score, Child-Pugh score, MRS, IgM, CRP, TNF- α , FGF-19, CK-18, C4, and ELF score will be summarized and analyzed using the Wilcoxon Rank Sum Test to compare treatment groups. The median differences and 95% CI of the median differences between treatment groups will be constructed using Hodges-Lehmann estimate. If the median differences between treatments are not symmetrical around the median, the Sign Test may be used.

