7.5.4. Assessing Cirrhosis

7.5.4.1. Determination for Dosing Regimen

To determine which dosing regimen subjects should follow, the presence or absence of cirrhosis should be assessed by the Investigator at Screening Visit 1. Acceptable methods of confirming (via medical history) or assessing cirrhosis for purposes of determining dosing is defined as a

subject who has documented evidence or presence of one or more of the following cirrhosis indicators:

Biopsy results consistent with PBC Stage 4 ([Ludwig 1978](#))

- TE Median Value ≥ 16.9 kPa ([Corpechot 2012](#))
- The presence of any of the following (unless exclusionary per [Section 8.3](#)) in the absence of acute liver failure:
 - Varices
 - Ascites
 - Radiological evidence of cirrhosis (nodular liver or enlargement of portal vein and splenomegaly)
- Combined low platelet count ($<140\,000/\text{mm}^3$) with:
 - persistent decrease in serum albumin, or
 - elevation in prothrombin time /INR (not due to antithrombotic agent use), or
 - elevated bilirubin ($2\times$ ULN)

Subjects who exhibit no evidence of cirrhosis by the above methods of assessment will be dosed using the Standard Dosing Regimen, while those who do exhibit evidence of cirrhosis by one or more of the above methods will be dosed using the Modified Dosing Regimen according to their Child-Pugh Score calculated in the electronic case report form (eCRF) (see [Appendix A](#) and [Section 7.3](#)).

Cirrhosis status should be reassessed as clinically indicated throughout the study. Any change in cirrhosis status will necessitate re-evaluation of the dosing regimen.

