8.3. Subject Exclusion Criteria

1. History or presence of other concomitant liver diseases including:
 - Hepatitis C virus infection
 - Active hepatitis B infection; however, subjects who have seroconverted (hepatitis B surface antigen and hepatitis B e antigen negative) may be included in this study after consultation with the Medical Monitor.
 - Primary sclerosing cholangitis
 - Alcoholic liver disease
 - Definite autoimmune liver disease or overlap hepatitis
 - Nonalcoholic steatohepatitis
 - Gilbert's Syndrome
2. Presence of clinical complications of PBC or clinically significant hepatic decompensation, including:
 - History of liver transplant, current placement on a liver transplant list, or current MELD score > 12 . Subjects who are placed on a transplant list despite a relatively early disease stage (for example per regional guidelines) may be eligible as long as they do not meet any of the other exclusion criteria.
 - Cirrhosis with complications, including history (within the past 12 months) or presence of:
 - Variceal bleed
 - Uncontrolled ascites
 - Encephalopathy

- Spontaneous bacterial peritonitis
 - Known or suspected hepatocellular carcinoma
 - Prior transjugular intrahepatic portosystemic shunt procedure
 - Hepatorenal syndrome (type I or II) or Screening (visit 1 or 2) serum creatinine >2 mg/dL (178 µmol/L)
- 3. Mean total bilirubin >5x ULN
- 4. Subjects who have undergone gastric bypass procedures (gastric lap band is acceptable) or ileal resection or plan to undergo either of these procedures.
- 5. Other medical conditions that may diminish life expectancy, including known cancers (except carcinomas *in situ* or other stable, relatively benign conditions such as chronic lymphatic leukemia).
- 6. If female: plans to become pregnant, known pregnancy or a positive urine pregnancy test (confirmed by a positive serum pregnancy test by the central laboratory), or lactating.
- 7. Known history of human immunodeficiency virus infection.
- 8. Medical conditions that may cause non-hepatic increases in ALP (eg, Paget's disease or fractures within 3 months).
- 9. Other clinically significant medical conditions that are not well controlled or for which medication needs are anticipated to change during the study.
- 10. History of alcohol abuse or other substance abuse within 1 year prior to Day 0.

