9.7.4. Day 0 Procedures (Randomization)

- Review inclusion and exclusion criteria for eligibility.
- Assess and record vital signs (weight, temperature, sitting heart rate, respiratory rate, and sitting blood pressure).
- Quality of Life and Subject questionnaires (see [Section 11.1.2.2](#) and [Section 12.2.5](#)).
- Perform TE at all study sites with access to Fibroscan® TE device. If TE has been done within 3 months of Day 0 and a report/adequate data are available, a pretreatment TE at Day 0 is not required. If the TE cannot be performed on Day 0 (eg, device/technician unavailability, scheduling issues, TE data is needed to inform cirrhosis assessment, etc), the procedure may be completed within the screening visit window, at Screening Visit 1 (if data is needed for cirrhosis assessment) or as close as possible to the Day 0 visit, preferably, after subject eligibility has been confirmed.
- Perform an esophagogastroduodenoscopy (endoscopy; at study sites, where the device is available) to assess the presence or absence of oesophageal varix/varices. If an endoscopy has been done within 12 months of Day 0 and a report/adequate data

are available, a pretreatment endoscopy at Day 0 is not required. If the endoscopy cannot be performed on Day 0 (eg, device/technician unavailability, scheduling issues, etc), the procedure may be completed within the screening visit window, as close as possible to the Day 0 visit, preferably, after subject eligibility has been confirmed.

- Subsequent endoscopies should be performed annually or per standard of care and the Investigator’s clinical judgment throughout the course of the study.
Endoscopies should also be performed when platelet counts are $<150 \times 10^9/L$.
- Assess and record any pretreatment-emergent AEs.
- Review and record prior concomitant medications.
- Review and record any nonstudy related medical or surgical treatment procedures and any medically relevant health care professional (HCP) or non-HCP related office visits that have occurred since the previous study visit.
- Randomize the subject only if s/he meets all inclusion criteria and no exclusion criteria.
- Verify that the subject has fasted for at least 8 hours.
 - Record fasting status in the source and CRF
 - If the subject reports having eaten within 8 hours, document accordingly in the source and CRF and remind the subject that fasting is required prior to all study visits.
- Obtain urine sample for urinalysis.

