11.1.2. Secondary Assessments

The following secondary efficacy assessments will be measured:

- Individual components of the primary endpoint
- Liver-related death
- Progression to cirrhosis as assessed by the presence of clinical, laboratory, or radiological evidence of cirrhosis and/or liver stiffness (Fibroscan® TE), confirmed by biopsy unless not medically indicated.

- Histological assessment of disease progression or improvement using paired biopsies in a subset of subjects (defined in Addendum 2).
- HCC confirmed by 2 complimentary imaging modalities, unless confirmed by biopsy.
- Liver biochemistry (see [Table 12](#) for list of analytes to be tested)
- Biomarkers, including other markers of hepatic fibrosis and/or inflammation, to be tested will include: IgM, c-reactive protein (CRP), tumor necrosis factor- α (TNF- α), FGF-19, cytokeratin-18 (CK-18) ELF, and Fibroscan (and others as determined during the course of the study).
- Clinical outcomes, including individual component of the primary endpoint (where available), liver transplant, and death will be compared to historical controls.
- PK of OCA and its conjugates.
- Data will be collected to inform quality of life and cost-effectiveness analyses that are relevant to major health care systems around the world. Quality of life will be assessed by questionnaires (PBC-40, EQ-5D-5L, and FIS) administered annually. Resource utilization information will be collected from the Medical and Surgical Treatment Procedures and Office Visit Log or other CRFs such as number, type and duration of hospitalizations, number of outpatient physician visits (subject reported), and use of concomitant medications.
- Endoscopy will be conducted at all study sites where the device is available to assess for the presence of oesophageal varix/varices at baseline. Throughout the study, any endoscopy performed as part of the annual study assessments or standard of care will be collected in the case report form to assess for the development of varix/varices.

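### Time to development of varices is analysed in the whole ITT population and censored at last contact, so subjects with baseline varices and subjects rarely or never scoped count as varices-free time and incidence is understated

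*Protocol*

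**What the plan says.** Section 13.1.5 opens its list with "The following time-to-event secondary efficacy analyses will compare OCA versus placebo using the ITT population" and includes "Time to development of varix/varices". It adds: "The same analysis methodology as used for the primary efficacy analysis will be used for these secondary efficacy analyses". That means the stratified log-rank test, Kaplan-Meier estimates and stratified Cox model of section 13.1.3. Section 13.1.1 defines ITT as everyone randomised who took any investigational product. Section 13.1.9.1 censors anyone without an event at last contact.

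Varices at entry are permitted. Section 8.3 excludes "Cirrhosis with complications, including history (within the past 12 months) or presence of" a list of complications that names variceal bleed but not varices. Section 7.5.4.1 lists varices among the indicators of cirrhosis used to choose the dosing regimen for enrolled subjects.

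On ascertainment, section 11.1.2 says: "Endoscopy will be conducted at all study sites where the device is available to assess for the presence of oesophageal varix/varices at baseline". It then says that later scopes, whether annual study scopes or standard of care, are recorded to assess development of varices. Section 9.7.4 accepts an endoscopy report from the 12 months before Day 0. It sets later scopes as annual or per standard of care and clinical judgment, and adds: "Endoscopies should also be performed when platelet counts are" below 150 × 10⁹/L. Table 2 schedules no endoscopy at EOT/EOS.

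**The concern.** An analysis of new varices needs two things: subjects free of varices at the start, and follow-up that counts only while someone is looking. The protocol collects the baseline endoscopy that would identify the first group but does not use it to define who is at risk. It also stops the clock at last contact rather than at last endoscopy. Section 8.4.1 lets a subject drop to semi-annual telephone contact or record review, so last contact can fall long after the last scope.

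A subject with varices at Day 0 thus sits in the risk set with no rule for what a Month 12 scope showing the same varices means. A subject never scoped is carried as varices-free to last contact. The same section shows the remedy for a neighbouring endpoint: progression to cirrhosis is restricted to subjects noncirrhotic at Baseline.

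At stake are the reported cumulative incidence of varices and, depending on how baseline varices are handled, the hazard ratio.

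**Working it through.** The protocol states no rate, effect size or event count for varices, so there is no figure to reproduce for this endpoint. The primary-endpoint figures (127 events, about 428 subjects) reproduce closely: 81.3% power with the two interim looks, and N of 427. They do not bear on this point.

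**Assumed inputs**
- Eight-year placebo incidence of varices, in subjects at risk and scoped: 20%. A second run used 30%.
- True hazard ratio: 0.60, borrowed from the primary endpoint's assumption in section 13.1.2.
- Share with varices at baseline, p: 0 to 20%.
- Share scoped, s: 60% to 100%.
- Exponential onset.

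**Incidence, baseline varices not counted as events**
- Among subjects at risk and scoped, six-year placebo incidence is 1 − 0.80^(6/8) = 15.4%.
- In the whole ITT population, with last-contact censoring, it becomes about (1 − p) × s × 15.4%.
- p = 0, s = 0.6: 0.6 × 15.4% = 9.2%.
- p = 0.2, s = 0.6: 0.8 × 0.6 × 15.4% = 7.4%.
- The 30% run behaves the same way at eight years. Simulation gave 24% with 20% prevalent, 18% with 40% never scoped, and 14% with both. The products are 0.8 × 30 = 24, 0.6 × 30 = 18 and 0.8 × 0.6 × 30 = 14.4.

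**Hazard ratio**

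The approximation is the ratio of log survival at eight years. OCA incidence among subjects at risk and scoped is 1 − 0.80^0.6 = 12.5%.

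| Handling of baseline varices | p, s | Placebo | OCA | ln(1 − OCA) / ln(1 − placebo) | Simulated Cox HR |
|---|---|---|---|---|---|
| Not counted | 0.2, 0.6 | 0.48 × 0.20 = 0.096 | 0.48 × 0.1253 = 0.060 | 0.0620 / 0.1009 = 0.61 | about 0.64 |
| Counted at first on-study scope | 0.1, 1.0 | 0.1 + 0.9 × 0.20 = 0.280 | 0.1 + 0.9 × 0.1253 = 0.213 | 0.2393 / 0.3285 = 0.73 | 0.74-0.77 |
| Counted, all prevalent cases scoped | 0.2, 0.6 | 0.2 + 0.48 × 0.20 = 0.296 | 0.2 + 0.48 × 0.1253 = 0.260 | 0.3013 / 0.3510 = 0.86 | 0.81-0.85 (this row and the next) |
| Counted, 60% of prevalent cases scoped | 0.2, 0.6 | 0.6 × 0.2 + 0.096 = 0.216 | 0.6 × 0.2 + 0.060 = 0.180 | 0.1986 / 0.2433 = 0.82 | as above |

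The simulations used annual detection and 6 to 10 years of follow-up. Their ranges reflect separate runs and simulation noise. Under the 30% assumption, large-sample simulation gave 0.61-0.63 when baseline varices were not counted. When they were counted it gave 0.71-0.78 with 10-20% prevalent and all others scoped, and 0.84 with 20% prevalent and 40% never scoped.

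So incidence is understated in proportion to (1 − p) × s whenever baseline varices are not counted. The hazard ratio moves materially only if they are.

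**The case against.** Four points on the other side have force.

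- **New onset is the natural reading.** The endpoint is named for development, and section 11.1.2 pairs a baseline scope for presence with later scopes for development. A reader might infer that the analysis dilutes a true 0.60 to about 0.8. The protocol nowhere says that baseline varices count as events, and on the new-onset reading the ratio stays near 0.60. The dilution is a risk left open, not a stated consequence.
- **Sites without the device are not blind to varices.** A reader might infer that their subjects can never have an event. Section 11.1.2 also records standard-of-care endoscopies, and section 9.7.4 calls for scopes when platelets are low. Ascertainment is incomplete and uneven, not absent.
- **The consequence is limited.** Section 13.1.10 makes tests on additional endpoints descriptive and exploratory. Randomisation should balance prevalent cases, so they do not inflate type I error. The missing EOT/EOS scope matters little if scopes are annual.
- **Some of this belongs in the SAP.** Derivation of one additional secondary endpoint is commonly settled there, and naming ITT does not forbid an at-risk subset, as the cirrhosis endpoint shows.

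The first three limit the size of the point. The fourth only partly answers it: the protocol itself fixes both the population and the censoring rule, and it gives no at-risk restriction for varices although it gives one for cirrhosis. Followed as written, those two rules produce the wrong denominator.

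**Conclusion.** The point holds as a minor to moderate one. The stated population and censoring rule credit subjects with baseline varices and subjects rarely or never scoped with varices-free time.

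Under the 20% assumption with 60% scoped, six-year placebo incidence falls from about 15% to 7-9% as baseline prevalence goes from 20% to 0%. The hazard ratio is about 0.60-0.65 against a true 0.60 if baseline varices are not counted, and about 0.75-0.85 if they are counted at the first on-study scope.

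All of these sizes rest on assumed incidence, prevalence and coverage. The documents give none of the three, and they support neither a definite bias in the hazard ratio nor a claim of false-positive risk from prevalent cases.

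**What to change.** For this endpoint, amend section 13.1.5 and the censoring rule in section 13.1.9.1, and carry the change into the SAP before unblinding:

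- Restrict the analysis to ITT subjects whose baseline endoscopy (Day 0, or the accepted report from the preceding 12 months) shows no varices. This uses pre-treatment information only, so the randomised comparison is kept.
- Censor subjects without an event at their last varices-free endoscopy instead of last contact.
- Report baseline and follow-up scope coverage by arm. Platelet-triggered and standard-of-care scoping may follow disease course, and the new censoring rule assumes that scoping is not informative.

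Do not make a post-baseline endoscopy a condition of inclusion. That would select on something that happens after randomisation and that treatment may affect. With last-scope censoring, a subject with no follow-up scope simply contributes no time at risk.

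The cost is wording only, with no new procedures. The downside is fewer subjects in this secondary analysis.
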